8.0 STUDY ASSESSMENT PROCEDURES

If a subject is unable to complete a specific assessment, this should be recorded in the eCRF and the subject's ability reassessed at the next specified visit. All attempts at performing assessments should be recorded. Any assessment may be repeated if the results are considered unreliable or of unacceptable quality by the Investigator.

All assessments will be conducted as indicated by the SOE

8.1 **Adverse Events**

Information regarding occurrence of AEs will be captured throughout the study. Duration (start and stop dates), severity/grade, outcome, treatment, and relationship to study drug will be recorded. Refer to Section 9.0, Assessment of Safety or Adverse Events and Serious Adverse Events, for further details.

8.2 **Laboratory Evaluations**

At Screening, laboratory results from the preceding QR421a study will be reviewed (if within the 12-week window), or a new local or central laboratory test, including a urine dipstick, will be performed to review for any abnormal laboratory values that may indicate a safety signal that would affect eligibility.

Subsequent laboratory evaluations will be conducted at a central laboratory and include serum chemistries, hematology and urinalysis. Reference ranges for all laboratory parameters are provided in the Laboratory Manual. See Appendix 2 for a list of laboratory tests to be conducted.

Serum chemistries will include sodium, potassium, chloride, bicarbonate, blood urea nitrogen (BUN), creatinine, glucose, calcium, phosphorus, alanine aminotransferase (ALT), aspartate aminotransferase (AST), gamma-glutamyl transferase (γGT), C-reactive protein (CRP), alkaline phosphatase (ALP), total and direct bilirubin, lactic dehydrogenase (LDH), albumin, and total

ProQR Therapeutics Page 36 of 65 protein. Estimated glomerular filtration rate (eGFR) is to be calculated using the CKD-EPI Creatinine Equation 2009 calculation.

Hematology will include a complete blood count (CBC): CBC with absolute differential (hematocrit, hemoglobin, white blood cell count [WBCs], red blood cell count, neutrophils, lymphocytes, monocytes, eosinophils, basophils, platelet count).

Coagulation panel: prothrombin time and International Normalized Ratio (INR).

Urinalysis (by visual inspection and dipstick) will include color and appearance, specific gravity, pH, protein, glucose, blood (erythrocytes), leukocytes, bilirubin, ketones, nitrite, and urobilinogen.

Repeat laboratory tests are permitted to confirm potentially spurious values or false positive results, at the discretion of the Investigator. Repeat analysis results for any laboratory assessments that may affect eligibility should be discussed with the Medical Monitor prior to subject inclusion.

For female subjects of childbearing potential, pregnancy testing will be performed per the SOE

8.3 **Systemic exposure**

Samples for systemic exposure analysis of QR-421a will be collected from all subjects as indicated per the SOE

8.4 **Ophthalmic Examinations**

Ophthalmic examinations include slit lamp biomicroscopy, intraocular pressure, and dilated fundus examination and will be performed according to the SOE Biomicroscopic examination includes pupillary examination, and examination of the external adnexa, conjunctiva, sclera, cornea, anterior chamber flare and cell score, iris, lens grading using the Age-Related Eye Diseases Study (AREDS) lens grading system, and vitreous examination. Intraocular pressure will preferably be assessed using Goldmann applanation tonometry. The same equipment should be used consistently throughout the study for a particular subject. Funduscopic examination (dilated) includes evaluation of optic nerve, macula, retinal vessels, and retinal periphery.

Following administration of study treatment, intraocular pressure and perfusion of the optic nerve head should be monitored and managed appropriately. Subjects should also be monitored for signs of inflammation during the post dosing period.

Further details on the procedures for ophthalmic examinations are in the Study Reference Manual.

ProQR Therapeutics Page 37 of 65

8.5 **Spectral Domain Optical Coherence Tomography**

Spectral domain optical coherence tomography (SD-OCT) will be performed according to the SOE - Changes in SD-OCT findings are of relevance to the safety and efficacy profile of QR-421a. All SD-OCT scans should be performed in accordance with the procedures outlined in the Imaging Manual.

8.6 **Efficacy Assessments**

Efficacy assessments include static and microperimetry, SD-OCT, BCVA, and LLVA, and will See the Study be performed at selected study visits as indicated in the SOE Reference Manual and Imaging Manual for further information on these assessments. All ophthalmic assessments will be performed on both the study and fellow eye. A central reading center will be used for several of the ophthalmologic assessments, including SD-OCT.

BCVA and LLVA will be assessed using the Early Treatment Diabetic Retinopathy Study (ETDRS) vision chart. LLVA will be measured by reading an ETDRS chart under normal lighting with a 2.0-log-unit neutral density filter placed in front of the best lens correction (Sunness 2008).

8.7 **Retinitis Pigmentosa Medical History**

The following information related to subjects RP due to mutations in exon 13 of the USH2A gene will be collected:

9.0 ASSESSMENT OF SAFETY OR ADVERSE EVENTS AND SERIOUS ADVERSE **EVENTS**

All subjects who receive study treatment will be assessed for safety.

Investigators are responsible for monitoring the safety of subjects who have entered this study and for alerting the Sponsor regarding any event that seems unusual, even if this event may be

ProQR Therapeutics Page 38 of 65

considered an unanticipated benefit to the subject. The Investigator is responsible for appropriate medical care of subjects during the study and may add unscheduled visits, additional exams/tests for safety purposes.

9.1 Definitions of Adverse Event, Serious Adverse Event, and Suspected Unexpected **Serious Adverse Event**

9.1.1 **Adverse Events**

An AE is any untoward medical occurrence associated with the use of a drug in humans, whether considered drug related or not. Adverse events can include any unfavorable, noxious, unintended sign, symptom, or disease temporally associated with use of a study drug or other protocolimposed intervention, regardless of attribution. Adverse events may be spontaneously reported by the subject, discovered by Investigator questioning, or detected through laboratory test, or other means.

Adverse events include:

- Pre-existing medical conditions judged by the Investigator to have worsened in severity or frequency or changed in character during the protocol-specified AE reporting period (as specified in Section 9.3.1)
- Adverse events not previously observed in the subject that emerge during the protocol-specified AE reporting period (as specified in Section 9.3.1)
- Complications that occur as a result of protocol-mandated interventions
- Adverse events that occur prior to study treatment that are related to a protocol-mandated intervention (e.g., invasive procedures such as blood draws, sedation prior to IVT injection)

9.1.2 **Serious Adverse Events**

An AE or suspected adverse reaction is considered "serious" if, in the view of either the Investigator or Sponsor, it results in any of the following outcomes:

- Death
- Life-threatening AE. This definition implies that the subject, in the view of the Investigator, is at immediate risk of death from the event as it occurred. It does not include an event that, had it occurred in a more severe form, might have caused death
- Inpatient hospitalization or prolongs existing hospitalization, except for planned hospitalization
- Persistent or significant disability/incapacity (i.e., the AE results in substantial disruption of the subject's ability to conduct normal life functions)

ProQR Therapeutics Page 39 of 65

- Congenital anomaly or birth defect. This serious criterion applies if a congenital anomaly/birth defect is diagnosed in a child born to a female subject, or a female partner of a male subject exposed to the study drug
- Other important medical events. Medical and scientific judgment should determine whether an AE should be classified as serious in other situations, such as important medical events that may not be immediately life threatening or result in death or hospitalization but may jeopardize the subject or require intervention to prevent one of the outcomes listed in the definition above.

All AEs that do not meet any of the criteria for serious should be regarded as non-serious AEs. Surgery for lens opacity removal (lens replacement) is not considered a serious AE as it does not require the subject be admitted to a hospital unit based on the nature of the surgery. Even in the case where the subject may be hospitalized for convenience, or a subject is too frail to make the commute back and forth to the surgical center, it is still not a Serious AE (SAE). The terms "severe" and "serious" are not synonymous. Severity refers to the intensity of an AE (as in mild, moderate, or severe pain); the event itself may be of relatively minor medical significance (such as severe headache) (see Section 9.2.1). "Serious" is a regulatory definition and is based on subject or event outcome or action criteria usually associated with events that pose a threat to a subject's life or vital functions. Seriousness (not severity) serves as the guide for defining regulatory reporting obligations.

Severity and seriousness should be independently assessed when recording AEs and SAEs on the AE eCRF and SAE form.

9.1.3 **Suspected Unexpected Serious Adverse Reaction Definition**

In order to be qualified as a suspected unexpected serious adverse reaction (SUSAR), the AE must meet 3 criteria: the event is serious, there is a certain degree of probability that the event is a reaction to the study drug being researched and the nature and severity of the reaction are not in agreement with the product information (i.e., the reaction is unexpected as per the reference safety information). All SUSARs will be reported as required to the Competent Authorities and to the Ethics Committee (EC)/Institutional Review Boards (IRBs) of the countries and centers concerned.

ProQR Therapeutics Page 40 of 65

9.1.4 **Adverse Events of Special Interest**

9.2 **Assessment of Adverse Events**

The Investigator is responsible for assessing the seriousness, severity and causality of AEs.

9.2.1 **Assessment of Severity (Intensity) of Adverse Events**

On the AE eCRF, the Investigator will use the adjectives MILD, MODERATE, or SEVERE to describe the maximum intensity of the AE. For purposes of consistency, these intensity grades are defined as follows:

- MILD: Does not interfere with subject's usual function.
- MODERATE: Interferes to some extent with subject's usual function.
- SEVERE: Interferes significantly with subject's usual function.

As described previously in Section 9.1.2, note the distinction between the severity and the seriousness of an AE. A severe event is not necessarily a serious event and may not meet the regulatory definition of serious. For example, a headache may be severe (interferes significantly with subject's usual function) but would not be classified as a serious AE unless it met one of the regulatory criteria for SAEs, listed above in Section 9.1.2.

ProQR Therapeutics Page 41 of 65 Any change in severity should be noted in the eCRF, e.g., a change from mild to severe or a change from severe to moderate should be noted with the start and stop dates for each intensity.

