4.0 STUDY OVERVIEW

4.1 **Criteria for Evaluation**

4.1.1 **Primary Endpoints**

- Incidence and severity of ocular adverse events (AEs)
- Incidence and severity of non-ocular AEs

4.1.2 **Secondary Endpoints**

- Change from baseline in the following outcome measures:
 - o Best Corrected Visual Acuity (BCVA)

ProQR Therapeutics Page 23 of 65

- Low Luminance Visual Acuity (LLVA)
- Static perimetry
- Ellipsoid Zone (EZ) area/width by spectral domain optical coherence tomography (SD-OCT)
- Microperimetry
- Exposure of QR-421a in serum

4.1.3 **Exploratory Endpoints**

4.2 **Study Design**

PQ-421a-002 is an open-label, extension study to evaluate the safety, tolerability, and efficacy of QR-421a in subjects with RP due to mutations in exon 13 of the USH2A gene.

Subjects that have participated in preceding QR-421a clinical studies, including study PQ-421a-001, will be given the opportunity to enroll into this extension study for continued dosing, provided the subject's benefit-risk assessment is positive, or for additional follow up. The Investigator, in consultation and agreement with the Medical Monitor, will decide on subject's enrollment upon assessment of subject's benefit-risk.

QR-421a will be first administered to the fellow eye and will be repeated every 6-month. Treatment of the study eye can commence as outlined in Section 6.1.5 and on the participant and when they completed their participation in the previous QR-421a study. The Investigator, in consultation and agreement with the Medical Monitor, will decide on dosing of both eyes. Continued subject treatment in this study will be pursued provided that the benefitrisk is positive for the individual subject, as discussed and agreed upon with the Medical Monitor.

The Sponsor, in consultation with the Investigator, may decide to modify the dose, the dosing interval for repeat injections in one eye or both eyes, hold the dose (delay or skip), or discontinue study drug for an individual subject, based on emerging safety and efficacy data and if it is anticipated to be in the best interest of the subject.

The same safety monitoring protocol and efficacy assessments will apply to both eyes.

ProQR Therapeutics Page 24 of 65

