Baseline functional and structural measurements for the study and fellow eye will be those from the Screening/Day 1 visit of the current study. Baseline functional and structural measurements from the previous QR-421a study, or historical clinical data, may also be used as part of the long-term safety and efficacy analysis.

Definition of Study Eye and Fellow Eye in Helia

Fellow eye is defined as follows: For subjects previously dosed (active or sham) in the preceding OR-421a study: the eye that was not selected as the study eye. For subjects that were not dosed at all: the eye with the worst BCVA at Helia Screening/Day1.

Study eye is defined as follows: For subjects previously dosed (active or sham) in the preceding QR-421a study: the eye that was selected as the study eye. For subjects that were not dosed at all: the eye with the best BCVA at Helia Screening/Day1.

4.2.1 **Study Plan**

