5.3 Eligibility Criteria

5.3.1 Inclusion Criteria

The subject is eligible for the study if all the following inclusion criteria apply at baseline:

- 1. Subjects who have participated in a preceding QR-421a study and who may derive benefit from continued treatment with QR-421a, and/or continued follow up, as assessed by the Investigator, in consultation and agreement with the Medical Monitor (Section 4.2.1.1).
- 2. An adult (≥ 18 years) willing and able to provide informed consent for participation prior to performing any study related procedures, and suitable verbal, auditory, written and/or tactile sign language communication as to allow informed consent to be obtained, in the opinion of the Investigator.

OR

A minor (12 to < 18 years) able to provide age-appropriate assent for study participation, and with a parent or legal guardian willing and able to provide written permission for the subject's participation prior to performing any study related procedures.

ProQR Therapeutics Page 28 of 65 24 May 2022

- 3. An adult willing to comply with the protocol, follow study instructions, attend study visits as required and willing and able to complete all study assessments. OR
 - A minor able to complete all study assessments and comply with the protocol and has a parent or caregiver willing and able to follow study instructions and attend study visits with the subject, as required.
- 4. Reliable BCVA, perimetry, and other measurements in both eyes, as described in the Study Reference Manual and Imaging Manual and determined by the Investigator.
- 5. Clear ocular media and adequate pupillary dilation to permit good quality retinal imaging, as assessed by the Investigator.

5.3.2 **Exclusion Criteria**

The subject is ineligible for the study if any of the following criteria apply at Screening:

- 1) Presence of any significant ocular or non-ocular disease/disorder (or medication and/or laboratory test abnormalities) which, in the opinion of the Investigator and with concurrence of the Medical Monitor, may either put the subject at risk because of participation in the study, may influence the results of the study, or the subject's ability to participate in the study. This includes but is not limited to a subject who has uncontrolled cystoid macular edema (CME) in the treatment eye. CME is permissible if stable for 3 months (with or without treatment). Past CME is permissible if resolved for more than 1 month.

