10.6 Subject Disposition, Demographics and Baseline Disease Characteristics

Subject disposition, baseline demographics and disease characteristics will be summarized for all subjects combined, and potentially grouped by baseline characteristics. Such grouping of subject disposition, demographics and disease characteristics by baseline characteristics will be described in the SAP.

10.7 **Treatment Compliance**

All doses are observed and administered by study staff. Treatment compliance will be determined by source records documenting treatment observations and summarized.

10.8 **Safety Analyses**

10.8.1 **Treatment Emergent Adverse Events**

A treatment-emergent AE (TEAE) is defined as an event that was not present prior to administration of the dose of study drug and present after the dose or if it represents the exacerbation of an event that was present prior to the dose.

Adverse events noted during the study will be coded to system organ classes (SOCs) and preferred terms (PTs) using the Medical Dictionary for Regulatory Activities (MedDRA) dictionary.

ProQR Therapeutics Page 48 of 65 The overall incidence of TEAEs will be classified by SOC and PT, and potentially summarized by groups based on baseline characteristics. Deaths, AE severity, seriousness, relationship to study drug will also be tabulated, potentially by groups based on baseline characteristics. If included, grouping based on baseline characteristics will be described in the SAP.

Ocular AEs will be presented separately for the study eye and the fellow eye.

10.8.2 **Other Safety Assessments**

Ophthalmology findings will also be summarized using descriptive statistics, frequencies, and percentages, and shifts from baseline, as appropriate. The number of subjects with a 10- and 15-letter decrease from baseline in BCVA will be tabulated.

10.9 **Systemic Exposure Analyses**

Systemic exposure will be estimated using standard methodology, if adequate serum concentrations of QR-421a are detected.

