5.6. Safety – Adverse events

A treatment-emergent AE (TEAE) is defined as an event that was not present prior to administration of the dose of study drug (ultevursen or sham-procedure) and present after the dose or if it represents the exacerbation of an event that was present prior to the dose.

Adverse events will be summarized by treatment group separately as follows:

- For non-ocular AE:
 - by subject, therefore, in any tabulation, a subject contributes only once to the count for a given adverse event (System Organ Class [SOC] or Preferred Term [PT]); and
 - During the overall study period (i.e., up to the last visit for the last subject).
 - Time to onset will be calculated in hours, relative to the last dose received, irrespective of which eye received the last dose (i.e., TE or CE).
- For ocular AE:

- by eye frequencies, separately for the TE and the CE, therefore, in any tabulation, an eye contributes only once to the count for a given AE (by SOC or PT). AEs that are reported in both eyes (i.e., OU) will be reported individually by eye in the tabular summaries; and
- During the overall study period (i.e., up to the last visit for the last subject).
- Time to onset will be calculated in hours, relative to the last dose received in the eye experiencing the ocular AE.

Unless otherwise stated, any summary of any type of TEAEs which includes the SOC and PT of the events will order the SOC and the PTs within the SOC by descending incidence of PT.

The following summary tables will be produced separately according to the type of AEs (ocular/non-ocular where applicable) as defined above:

- Overview of Ocular Adverse Events for Treatment Eye during the overall study period (Safety Population)
- Overview of Ocular Adverse Events for Contralateral Eye during the overall study period (Safety Population)
- Overview of Non-Ocular Adverse Events during the overall study period (Safety Population)
- Summary of Ocular Treatment-Emergent Adverse Events for Treatment Eye during the overall study period by MedDRA System Organ Class and Preferred Term (Safety Population)
- Summary of Ocular Treatment-Emergent Adverse Events for Contralateral Eye during the overall study period by MedDRA System Organ Class and Preferred Term (Safety Population).
- Summary of Non-Ocular Treatment-Emergent Adverse Events during the overall study period by MedDRA System Organ Class and Preferred Term (Safety Population).
- SAEs
- AESIs

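### Ocular AE severity is graded on the whole subject's function but presented by eye, so a grade can understate a marked vision loss in one eye

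*Protocol*

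**What the plan says.** Protocol 9.2.1 gives one three-grade scale for all AEs. The lowest grade reads "Does not interfere with subject's usual function" and the highest "Interferes significantly with subject's usual function"; MODERATE sits between them with the same reference point. The visible text of the two documents contains no separate grading rule for ocular events and does not define usual function.

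Protocol 4.1.1 makes both incidence and severity of ocular AEs the first primary endpoint. It names no unit, but the analysis sections do. Protocol 10.8.1 states "Ocular AEs will be presented separately for the study eye and the fellow eye", and SAP 5.6 reports ocular AEs as "by eye frequencies, separately for the TE and the CE". SAP 5.6 also splits an AE reported in both eyes into one entry per eye in the tables, without asking for a grade per eye.

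Three design features bear on this:
- Entry requires "Reliable BCVA, perimetry, and other measurements in both eyes" (Protocol 5.3.1).
- Eyes are dosed in sequence: "QR-421a will be first administered to the fellow eye and will be repeated every 6-month" (Protocol 4.2), with study-eye dosing starting at Month 3 or Month 9 (Protocol 7.2).
- For subjects not dosed before, the fellow eye is "the eye with the worst BCVA at Helia Screening/Day1" (Protocol 4.2). For subjects dosed before, the eye labels carry over from the preceding study.

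Severity is also one of the named considerations when treatment is stopped for an individual (Protocol 4.2.2.1).

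**The concern.** The grade belongs to the person, but the result is reported for the eye. If a subject loses a good deal of vision in one eye and carries on as usual with the other, an investigator following 9.2.1 as worded can record MILD, and the table or listing then shows MILD against an eye that has lost substantial function. The same loss in a subject whose other eye is poor could be graded higher.

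A by-eye severity grade is then partly a statement about the eye that had no event. A reader could not tell a trivial MILD event from a marked one-eye loss, on a component of the primary endpoint and on an input to individual stopping decisions. The sequential dosing makes events in one eye only an expected scenario, not a rare one.

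**Working it through.** The plan gives no figure on this point, so there is none to reproduce, and no calculation from the documents yields a frequency. The check sets the passages side by side.

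**1. Unit of grade against unit of report**

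| Element | Place | Unit |
|---|---|---|
| Severity is part of a primary endpoint | Protocol 4.1.1 | not stated |
| MILD, MODERATE, SEVERE | Protocol 9.2.1 | subject |
| Presentation of ocular AEs | Protocol 10.8.1 | eye |
| Count of ocular AEs | SAP 5.6 | eye |

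The grade and the report use different units, and no visible rule converts one to the other.

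**2. When the mismatch can change a grade.** Three conditions must all hold: the event acts mainly through vision loss; the other eye can sustain what the subject usually does; and the investigator judges interference on that basis. Protocol 5.3.1 makes the second condition plausible, since both eyes must be measurable at entry. The third is a matter of judgment that the documents do not settle.

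**3. Illustration of the mechanism (assumed values throughout).** Suppose, as a simplification, that usual function followed the acuity of the better eye. Let B be the better eye, W the worse eye and L the loss, in letters.
- Loss in the worse eye: max(B, W − L) = B, so the change is 0.
- Loss in the better eye: max(B − L, W), so the drop is min(L, B − W).

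With B = 75 and L = 20:

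| W | Loss in worse eye | Loss in better eye |
|---|---|---|
| 55 | max(75, 35) = 75, drop 0 | max(55, 55) = 55, drop 20 |
| 65 | max(75, 45) = 75, drop 0 | max(55, 65) = 65, drop 10 |
| 75 (equal eyes) | max(75, 55) = 75, drop 0 | max(55, 75) = 75, drop 0 |

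Under that simplification an identical 20-letter loss costs the subject anywhere from 0 to 20 letters, depending only on the other eye. With equal eyes the loss is hidden whichever eye is affected. The table shows how the mechanism works; it says nothing about how often it operates.

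**4. Whether another provision repairs the grade**
- Seriousness is assessed independently of severity (Protocol 9.1.2), and its category of other important medical events could make a large one-eye loss an SAE. The severity grade stays as it was. The disability criterion is itself worded at subject level.
- Protocol 10.8.2 tabulates 10- and 15-letter BCVA decreases, but as numbers of subjects, and that table is not among those SAP 6 retains.
- SAP 5.7 lists ocular AEs and BCVA, but as separate listings.
- Protocol 9.3.3 has a persistent AE recorded again only if it becomes more severe or more frequent. A one-eye loss that deepens while usual function holds may not meet that condition.

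None of these changes the recorded severity.

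**The case against.** The strongest reply is that a single scale of impact on the person, used for all AEs, is a defensible choice, and that little can be built on the mismatch. Much of this stands.

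- A reader might infer that 9.2.1 forces a MILD grade for any one-eye loss the other eye covers. It does not. Usual function is undefined, and a subject who notices marked loss in one eye may well report some interference, which is MODERATE. Protocol 2.1 describes a disease of night vision and peripheral field in which central vision goes last, so better-eye acuity is only a rough stand-in for function.
- A reader might infer that every unilateral ocular AE is affected. That is too broad. Protocol 2.3 names raised intraocular pressure and intraocular inflammation among the monitored risks. A good fellow eye does not offset pain, and a symptomless pressure rise would be MILD in either eye.
- A reader might infer a bias in the drug's favour, with fellow-eye grades too low. The documents do not support this. The worse-eye definition covers only subjects not dosed before, and the visible text does not say how the preceding study chose its study eye. The study is open-label and descriptive, SAP 6 plans no formal analysis, and no study-eye versus fellow-eye severity comparison is planned.
- Eye-specific guidance may sit in the AESI section, the form completion guidelines or the Study Reference Manual, whose text is not available here. The SAP names no severity table, and its output shells are in a separate document.
- The listings already let a reader match BCVA to an event by hand, and a protocol sentence cannot change grades already given.

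What remains is the mismatch itself. The scale refers to the subject, the report refers to the eye, and the listed safeguards leave the grade untouched.

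**Conclusion.** The concern holds in a limited form. For ocular AEs whose main effect is vision loss that the other eye can offset, the 9.2.1 grade can depend on the other eye and understate a marked loss in the affected eye. Where this acts, it lowers the grade of that event, but its frequency is unknown and could be small. It does not extend to events that the other eye cannot offset, and it establishes no direction between study eye and fellow eye beyond the fact that, in subjects not dosed before, the fellow eye is the one with worse BCVA.

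The point concerns marked loss, not serious loss: the protocol keeps seriousness as a separate regulatory judgment, and one event could be both MILD and serious. The conclusion assumes that no eye-level grading rule exists in the manuals or the withheld text. It does not undermine AE incidence. It is a worthwhile, low-cost improvement to how the severity part of the endpoint can be read.

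**What to change.** In Protocol 9.2.1, or in wording carried into a later protocol, state that for ocular AEs *function* means the visual function of the affected eye and that bilateral events are graded separately for each eye. Keep the present wording for non-ocular AEs.

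SAP 2.2 and SAP 6 show that the study stopped early and is closing out, so the part that can still be carried out is in the outputs. Do not regrade. In the ocular AE listing under SAP 5.7, add the affected eye's BCVA change from baseline at the measurement nearest the event, beside the severity grade, with the measurement date so that a value taken before onset is recognisable. Visits are 3 or 6 months apart, so the nearest value may be some weeks from the event.

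The cost is one sentence and the added listing columns, from data already collected. The downsides are slightly less comparability of grades with the preceding study, if that study used the subject-level wording, and some added investigator judgment in separating one eye's function from the subject's.
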